5.1. Safety Population/ Intent-to-treat Population

The safety/intent-to-treat (ITT) population consists of all patients with an eligible FGFR1–3 GA who received at least one dose of derazantinib or atezolizumab. Safety data will be summarized according to the treatment actually received.

In the primary safety comparison, patients who crossover to derazantinib-atezolizumab combination are censored at time of crossover (i.e., AEs occurring during treatment with derazantinib-atezolizumab combination are excluded for Cohort 4a patients).

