8.2.1 Safety analysis population / Intent-to-treat population

The Safety / Intent-to-treat population consists of all patients with an eligible *FGFR1-3* GA who received at least one dose of derazantinib or atezolizumab. Safety data will be summarized according to the treatment actually received.

In the primary safety comparison, patients who crossover to derazantinib-atezolizumab combination are censored at time of crossover (i.e., AEs occurring during treatment with derazantinib-atezolizumab combination are excluded for Cohort 4a patients). An exploratory safety analysis will be conducted for the crossover population including all safety events starting from the date of the first dose of derazantinib-atezolizumab combination.

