Substudy 1 uses a Simon's two-stage design. In Stage 1, 35 evaluable patients will be enrolled. The decision to transition from Stage 1 to 2 will use all data collected in stage 1 to inform the decision and the decision will be taken according to the principles laid out in the IDMC charter. If 7 or fewer patients with an objective response (defined as a CR or PR) are observed in Stage 1, the cohort will be stopped. If 8 or more patients with an objective response are observed in these 35 patients, an additional 39 patients will be enrolled, for a total of 74 patients. The null hypothesis will be rejected if 22 or more responses are observed in these 74 patients.

Substudy 2

This substudy will enroll patients with any advanced solid tumor and any prior treatment (including FGFR inhibitor treatment), who have no standard treatment alternative. Patients in this substudy are to receive derazantinib-atezolizumab in combination, with the primary objective of identifying the appropriate recommended Phase 2 dose (RP2D) of the derazantinib-atezolizumab combination to be used in Cohort 3b and Cohort 4b. Assignment to a specific dose level and cohort will be controlled by the IWRS system.

This substudy is a safety run-in using a modified rolling-six design including up to 24 patients in two dose cohorts. If none or 1 of six patients in the dose-level 1 cohort (200 mg derazantinib QD plus 1,200 mg atezolizumab Q3W) experiences a DLT in Cycle 1, dose level 1 will be considered tolerable. The dose-level 1 will then be expanded by additional 6 patients (expansion cohort for dose level 1) to further characterize the safety and tolerability profile. In addition, the dose-level 2 cohort (300 mg derazantinib QD plus 1,200 mg atezolizumab Q3W) will start enrollment with an initial target sample size of 6 patients. If dose level 2 is considered tolerable, then dose level 2 will be expanded by additional 6 patients to further characterize the safety and tolerability profile of this dose level. The sample size may increase if there is a need to explore further intermediate dose levels.

The RP2D will be declared based on observed AEs by a joint decision taken by the IDMC, Investigators, and the Sponsor.

3.2. Substudy 3

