5.2. Modified Intent-to-treat (mITT) Population

For all efficacy endpoint analyses, a mITT population will be used, comprising all patients who received at least one dose of derazantinib or atezolizumab, and have at least one post-baseline imaging assessment in accordance with RECIST 1.1, or documented clinical progression (every effort should be made to objectively assess radiographic progression) or death. Non-evaluable patients will be replaced.

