6.3. Efficacy Analysis

All efficacy endpoints will be summarized by substudy and cohort. P-values and 95% CIs will be provided where appropriate. Comparisons between cohorts of substudy 4 will be performed using descriptive statistics and for the purposes of hypothesis generation only.

All efficacy analyses will be conducted using the mITT population. To evaluate sensitivity, the primary efficacy analyses (i.e. Section 6.3.1), will also be conducted using the PP population.

Assessments by Blinded Independent Central Review (BICR) consider two readers. Should there be disagreement between these two readers, an adjudicator decides which reader is correct. As such, all analyses which consider BICR assessments will be based upon the first reader by default, unless the second reader is selected following adjudication.

Per protocol inclusion criteria, only patients with measurable disease by RECIST version 1.1 criteria should be enrolled. If a patient without measurable disease is enrolled, the ITT principle requires including these patients in the analyses. Hence, analyses will be based on patients with either measurable or non-

measurable disease. For this purpose, non-CR/non-PD in patients with non-measurable disease will be considered equivalent to SD in patients with measurable disease, and the same rules will be applied.

Waterfall plots, spider plots and swimmer plots will be produced to accompany efficacy analyses.

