6.4. Safety Analysis (All substudies)

All safety analyses will be performed using the safety/ITT population, apart from in the analysis of DLTs in substudy 2 which will be performed using the MTD population (see Section 5.4). Analyses will be presented by substudy and cohort.

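### The combined Safety/ITT set requires an eligible FGFR1–3 aberration, so a dosed patient without one is left out of the summary safety and exposure tables

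*SAP*

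**What the plan says.** SAP 5.1 sets two conditions for the Safety/ITT set: "all patients with an eligible FGFR1–3 GA who received at least one dose of derazantinib or atezolizumab". Protocol 8.2.1 has the same two. It opens with "The Safety / Intent-to-treat population consists of all patients with an eligible" FGFR1–3 aberration and continues "who received at least one dose of derazantinib or atezolizumab. Safety data will be summarized according to the treatment actually received". The protocol synopsis repeats this.

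SAP 6.4 gives the set its reach: "All safety analyses will be performed using the safety/ITT population, apart from in the analysis of DLTs in substudy 2", which uses the MTD population of SAP 5.4. SAP 6.2.9 puts exposure and compliance on the same set. So do SAP 6.2.2 (protocol deviations) and SAP 6.6 (patient-reported outcomes).

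The efficacy set is built differently. SAP 5.2 describes mITT as "comprising all patients who received at least one dose of derazantinib or atezolizumab, and have at least one post-baseline imaging assessment", or clinical progression or death, and names no aberration. SAP 6.3 then says "All efficacy analyses will be conducted using the mITT population".

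The SAP also covers Substudy 2, which its Study Design section describes thus: "This substudy will enroll patients with any advanced solid tumor and any prior treatment". No aberration requirement is stated there. Protocol 1.4.1.2 reports the Substudy 2 ITT and Safety populations as 26 patients.

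**The concern.** A safety set should describe everyone exposed to the drug, and tumor genotype does not alter exposure. With a molecular entry criterion inside the definition, a patient dosed without an eligible aberration leaves both numerator and denominator of the adverse event, laboratory, ECG and exposure summaries. Such a patient is also missing from the deviation summary in SAP 6.2.2, the table that would otherwise report the error.

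The sets are also not nested. A patient can contribute to the response rate and yet be absent from the safety tables for the same cohort. For Substudy 2, the definition read literally does not match how the documents themselves count patients.

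**Working it through.** This is a question of set definitions. The only Safety/ITT count in the documents is the one for Substudy 2, so that comes first.

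**1. The plan's own figure (Protocol 1.4.1.2).**
- By dose level: 14 + 12 = 26.
- By part: MTD cohorts 7 + 6 = 13, expansion cohorts 7 + 6 = 13, and 13 + 13 = 26.

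The reported Safety/ITT count equals the number enrolled. No aberration filter is visible in it.

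**2. Nesting.** Let D = dosed, G = eligible aberration, I = post-baseline imaging, C = clinical progression, X = death.
- Safety/ITT (SAP 5.1) = D ∩ G
- mITT (SAP 5.2) = D ∩ (I ∪ C ∪ X)
- In mITT but not in Safety/ITT = D ∩ (not G) ∩ (I ∪ C ∪ X)

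The last set contains every dosed patient without an eligible aberration who is scanned, progresses clinically or dies. Protocol 8.2.2 lacks the death route but also has no aberration clause, so the result is the same there. If Safety is simply D, mITT is a subset of it by construction.

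**3. Where such a patient appears.**

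| Output | Set | Included? |
|---|---|---|
| AE summaries, including TEAE leading to death (SAP 6.4.1) | Safety/ITT | No |
| Exposure and compliance (SAP 6.2.9) | Safety/ITT | No |
| ORR and other efficacy (SAP 6.3) | mITT | Yes, if in mITT |
| Overall survival (SAP 6.3.2.4) | mITT | Yes, if in mITT |
| By-patient AE listings (SAP 6.4.1) | All on-study AEs | Yes |
| Substudy 2 DLT analysis (SAP 5.4, 6.4) | MTD population | Yes, if criteria met |

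**4. Substudy 2 under the literal wording.** The Safety/ITT count would be 26 × g, where g is the share with an eligible aberration. The documents do not give g, so the values below are assumptions for illustration.
- g = 15%: 26 × 0.15 = 3.9, about 4
- g = 20%: 26 × 0.20 = 5.2, about 5
- g = 50%: 26 × 0.50 = 13
- g = 100%: 26

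Only g = 100% reproduces the reported 26. SAP 5.4 points the same way: it keeps Substudy 2 patients who are not evaluable for DLT in Safety/ITT and attaches no aberration condition.

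**5. Substudies 1, 3, 4 and 5.** An eligible positive test is inclusion criterion 5 (Protocol 4.2), so only enrollment errors are affected. The documents give no error rate. For scale, one such patient is 1/74 = 1.4% of a full Substudy 1 or 1/26 = 3.8% of a full Substudy 5.

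**6. PK set.** SAP 5.5 builds it on ITT, so it inherits the clause. Protocol 8.2.4 asks only for one derazantinib dose and one sample. SAP 6.8, which lists changes from the protocol, does not mention the difference.

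**7. A contrary rule in the same SAP.** SAP 6.3 keeps a patient enrolled without measurable disease in the analyses, on intent-to-treat grounds. SAP 5.1 does the reverse for a molecular entry error, in the set that carries the ITT name.

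**The case against.** The strongest reply is that the clause only restates an entry criterion. Protocol 5.2.1.3 forbids enrolling ineligible patients, a local NGS result by itself establishes eligibility (Protocol 3.1.1), and no later re-adjudication of that result is described. For Substudy 2, Protocol section 8 says it covers active substudies only, so the clause was not written for that substudy and SAP 5.1 carried it over. This stands as far as it goes. It makes the number affected in the active substudies small, possibly zero, and makes the Substudy 2 conflict one of wording. It does not make the definition right: entry errors are the case in which a safety set must still count the patient.

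A reader might infer more than the documents support:

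- **That all death reporting is affected.** It is not. Overall survival runs on mITT, and only the TEAE-leading-to-death summary depends on Safety/ITT.
- **That serious events would be hidden.** Listings cover all on-study AEs, SAEs go to the sponsor within 24 hours (Protocol 7.4.3.2), and the IDMC reviews safety in enrolled patients (Protocol 3.5). None of these depends on the set definition. What is lost is the patient's place in the summary tables.
- **That the Substudy 2 safety set would be nearly empty.** The range of 0 to 26 is a logical bound. The documents' own count is all 26.
- **That a definite number is lost in the active substudies.** Any percentage applied to planned enrollment would be an assumption with no source in the documents.
- **That the interim DLT evaluations in Substudies 3 and 5 would drop patients.** SAP 6.4 does not exempt them, but SAP 6.4.2 refers to the first 10 enrolled in each, so that reading is not secure.

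**Conclusion.** The definition is wrong as written in both documents. A dosed patient without an eligible aberration is left out of the summary safety and exposure tables, while remaining eligible for mITT, overall survival and the AE listings. In Substudies 1, 3, 4 and 5 the effect is confined to enrollment errors, of unknown and possibly zero number. In Substudy 2 the literal rule fits the reported 26 patients only if all of them had an eligible aberration, which the documents do not say. The primary efficacy tests are untouched, because they run on mITT. The conclusion rests on reading SAP 5.1 literally and on the absence of any stated aberration requirement in the SAP's description of Substudy 2. It is worth correcting because the change is small and makes the safety tables cover everyone exposed.

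**What to change.** - In SAP 5.1, Protocol 8.2.1 and the protocol synopsis, define the Safety population as every patient given at least one dose of either study drug, summarized by treatment received, with no aberration clause. Substudy 2 then stays at 26, and mITT lies inside the Safety population.
- In SAP 5.5, build the PK set on that Safety population. This agrees with Protocol 8.2.4, which has no aberration clause.
- Leave mITT without an aberration criterion. Adding one would remove treated patients from the primary response analysis and, through the replacement rule, could change who is replaced. If an aberration-eligible set is wanted, define it under its own name as supportive.

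The cost is a few sentences in two documents. No new data are needed.

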5.2. Modified Intent-to-treat (mITT) Population

For all efficacy endpoint analyses, a mITT population will be used, comprising all patients who received at least one dose of derazantinib or atezolizumab, and have at least one post-baseline imaging assessment in accordance with RECIST 1.1, or documented clinical progression (every effort should be made to objectively assess radiographic progression) or death. Non-evaluable patients will be replaced.

5.3. Per-protocol (PP) Population

The PP population will include all patients in the mITT population who have no major protocol deviations which are determined to potentially impact efficacy analyses during the study. Protocol deviations will be identified prior to final analysis.

This analysis population will be used for secondary analysis of primary and secondary endpoints.

5.4. Maximum-tolerated Dose (MTD) Population (Substudy 2 only)

The MTD-determining population includes all patients enrolled in the MTD Part of each dose level who meet the following minimum criteria during the DLT period:

- received at least one dose of derazantinib and atezolizumab and has experienced a DLT;
- received $\geq 90\%$ of the derazantinib and atezolizumab dose, respectively, in Cycle 1 and did not experience a DLT, have been observed for ≥ 21 days following the first dose, and have been evaluated for safety.

In the event that Cycle 1 exceeds 21 days, the period for patient's evaluability and DLT assessment will remain at 21 days.

Patients who do not meet these minimum evaluation requirements will be regarded as ineligible for the MTD-determining population. These patients will be included in the safety/ITT population but will be excluded from the calculation of DLT incidence and will be replaced by recruitment of additional patients.

Interim analyses for DLTs may be performed once at least five patients have been enrolled to a particular dose level, full DLT/safety data are available and a patient has not experienced a DLT, or when two DLTs have been observed in any number of patients enrolled in MTD Part of a particular dose level, whichever occurs first. Interim analyses are performed to determine if dose escalation is justified (or dose de-escalation is required) and if derazantinib in combination with atezolizumab is safe and tolerable.

5.5. Pharmacokinetic (PK) analysis population

The PK analysis population consists of all patients in the ITT population who have at least one PK sample result. Three sub-populations are defined, according to the analytes and sampling schedule:

- The Rich derazantinib PK profiling population (with PK parameter determination) consists of the patients enrolled in the rich sampling schedule (see Section 5.3.4.1.2 of the protocol) who receive at least 1 dose of study drug and have at least one PK sample result.
- The Sparse derazantinib PK sampling population consists of the patients enrolled in the sparse sampling schedule (see Section 5.3.4.1.3 of the protocol) who receive at least 1 dose of study drug and have at least one PK sample result.
- The atezolizumab PK population (see Section 5.3.4.2 of the protocol) consists of all patients who receive at least 1 dose of atezolizumab and have at least one PK sample result.

6. Statistical Methodology

6.1. Statistical and Analytical Issues

6.1.1. Statistical Methods

Tabulations will be produced for appropriate demographic, baseline, safety and efficacy parameters. Continuous variables will be summarized by reporting the number of observations, mean, standard deviation, median, first quartile (Q1), third quartile (Q3), minimum, and maximum. Categorical variables will be summarized using frequency tables showing the number and percentage of patients within a particular category, where the denominator is the number of patients within the category at applicable time point (unless otherwise specified). Time-to-event data will be summarized using the Kaplan-Meier method.

By-patient data listings will be produced for data collected through the study (e.g., CRF, lab). All data listings that contain an evaluation date will contain a relative study day (Study Day). Pre-treatment and on-treatment study days are numbered relative to the day of the first dose of study medication, which is designated as Day 1. The preceding day is Day -1, the day before that is Day -2, etc. Baseline will be defined as the last evaluable/non-missing observation/assessment prior to the first dose of study drug on Cycle 1, Day 1.

Statistical analyses will be carried out by using SAS Version 9.4 or higher. Any deviations from the planned analysis as described in the SAP will be justified and recorded in the clinical study report.

Adverse events will be graded by the Investigator based on the National Cancer Institute (NCI) Common Terminology Criteria for Adverse Events (CTCAE), Version 5.0, and will be coded for summarization using the Medical Dictionary for Regulatory Activities (MedDRA® Version 22.0 or later). Concomitant medications will be coded using the World Health Organization (WHO) Drug Dictionary (March 2019 version or later).

6.1.2. Dose Level, Substudy, and Cohort Assignment

The definition of cohort and substudy in this study are detailed in Section 3. All analyses will be summarized by substudy and cohort (Substudies 1, 3, 4 and 5) or by dose level (Substudy 2)

6.1.3. Visit Windows

All data will be tabulated per the evaluation visit as recorded on the eCRF, even if the assessment is outside of the visit window. Unless otherwise stated in the analysis sections below, unscheduled visits will be included in data listings only.

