These assessments must be reviewed prior to dosing, and study drug administration should only occur if local laboratory test values are acceptable (i.e., CTCAE grade 2 or less), unless dose delays or modifications are clinically indicated (as assessed by the Investigator and agreed upon by Medical Monitor or designee; see Section 6.1.1.5).

Safety laboratory determinations will include hematology, blood chemistry, liver function tests, and coagulation tests. If clinically indicated, some or all of these tests may be repeated on other study days.

Clinical safety laboratory tests will comprise the following:

- **Hematology:** complete blood count including hemoglobin, hematocrit, absolute white blood cell count with 5-part differential, red blood cell count, and platelet count
- **Blood chemistry:** albumin, calcium, magnesium, chloride, C-reactive protein (CRP), creatinine, glucose, phosphate, potassium, amylase, lipase, total protein, sodium, thyroid panel (TSH, fT3, fT4), uric acid, and Vitamin D
 - CRP is required at C1D1 only and thereafter if infection is suspected;
 - CL_{CR}, as calculated by the Cockcroft-Gault equation (at the Screening Visit only);
 - TSH, fT3 and fT4 is required at C1D1 and subsequently every 4 cycles;

- 25-hydroxy vitamin D is required at C1D1, C3D1, C5D1, and the End of Treatment visit only.
- **Liver function tests:** ALT, AST, Alkaline phosphatase (ALP), total and direct bilirubin, lactate dehydrogenase
- **Coagulation tests:** prothrombin time, INR, and partial thromboplastin time (at the Screening and End of Treatment visits, and if clinically indicated at any time during treatment)

Additional testing may be performed whenever clinically indicated at the discretion of the Investigator and if applicable in relation to the patient's medical history. All samples for a given study center must be analyzed by the same local laboratory throughout the study, as designated by the Investigator. The results are to be printed, signed and dated by the Investigator or their designee.

In the event of unexplained abnormal laboratory test values, the tests must be repeated immediately and followed-up until return to the normal range, stabilization, and/or until an adequate explanation of the abnormality has been determined. Abnormal laboratory results should not be recorded as an AE unless the abnormality is associated with a clinically-relevant condition (see Section 7.4.3.1.1).

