5.3.3.2.4 RECIST 1.1 and iRECIST

The efficacy of derazantinib monotherapy treatment and derazantinib-atezolizumab in combination will be primarily measured by ORR evaluated by BICR using RECIST 1.1 (see [Appendix 2](#)).

In addition, an exploratory assessment will be performed using iRECIST criteria ([Seymour 2017](#)) in patients treated with derazantinib-atezolizumab in combination, including those patients undergoing crossover treatment (see [Appendix 3](#) for comparison of RECIST 1.1 and iRECIST).

The iRECIST criteria is RECIST 1.1 adapted to account for the tumor response patterns seen with immunotherapeutic drugs. In patients undergoing combination treatment with derazantinib and atezolizumab, iRECIST will be used by the site Investigator / local

radiology review to assess tumor response and progression, and to make treatment decisions. These data will be collected in the clinical database. Treatment efficacy based on iRECIST as assessed by central imaging vendor review will be evaluated retrospectively.

The Investigator should make every attempt to perform the confirmation scan of CR or PR 4–5 weeks after the last scan was performed. The confirmation scan of iUPD should be performed 4–8 weeks after the last scan was performed, unless criteria for clinical stability are not met (see below).

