In alignment with interventions to ensure patient safety and for the purpose of this protocol, hyperphosphatemia is defined as:

- Grade 1: > ULN to < 7.0 mg/dL (< 2.26 mmol/L)
- Grade 2: Non-invasive intervention required (e.g., withhold drug or modify dose) or between 7.0 – 9.0 mg/dL (2.26 – 2.90 mmol/L)
- Grade 3: Severe or medically significant, but not immediately life threatening or > 9.0 – 10.0 mg/dL (> 2.90 – 3.23 mmol/L)
- Grade 4: Life-threatening consequences, urgent intervention indicated e.g., dialysis or > 10.0 mg/dL (> 3.23 mmol/L)

Patients who present with serum phosphate ≥ 7.0 mg/dL, adding an oral phosphate binding/reducing agent¹ until serum phosphate level returns to < 5.6 mg/dL should be considered, and patients should be instructed to adhere to a low-phosphate diet.

6.1.1.5.2 *Management of retinal adverse events*

A complete ophthalmological examination (see Section 5.3.2.3) should be performed by an ophthalmologist at the Screening visit, for the first four cycles (i.e., Day 1 of Cycles 2–5), and at the End of Treatment visit. Further complete ophthalmological examinations only need to be performed if clinically indicated. [Table 5](#) provides specific guidance for the management of dose delays/reductions in the case of retinal adverse events possibly related to derazantinib.

6.1.1.5.3 *Management of QTc prolongation or other significant ECG abnormalities*

If significant QTc prolongation and/or significant ventricular arrhythmia is observed, i.e., a prolonged QTcF interval ≥ 501 ms on at least two separate ECGs (mean values from triplicate ECGs, consistent with a CTCAE grade 3 event), the patient must be monitored by the Investigator and hourly (triplicate) 12-lead ECG obtained until the mean QTcF has returned to ≤ 450 msec for males or to ≤ 460 msec for females. The clinical context and possible factors contributing to QTc prolongations such as electrolyte abnormalities (potassium, calcium or magnesium), concomitant medications, or other clinical factors such as cardiac ischemia must be carefully assessed, and any findings documented in the eCRF. The decision to continue treatment with derazantinib should be reviewed and supported by a cardiologist.

¹ Either calcium-containing (e.g., calcium carbonate and calcium acetate) or non-calcium-containing (e.g., sevelamer) phosphate binders, and/or phosphaturic agents, depending on serum calcium levels and in accordance with institutional guidelines, recommendations, and schedules.

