6.4.5. Electrocardiogram

The actual value and change from baseline to each visit and at end of study will be descriptively summarized by visit for ECG parameters (e.g., heart rate, RR interval, PR interval, QRS duration, QT interval, QTcF interval and QTcB interval). For all patients, a standard, triplicate, 12-lead ECG must be performed at all study visits using the pre-programmed device provided by the Sponsor. Summary tables will consider the mean of the triplicate measurements at each visit as the single reported value.

A categorical analysis of QTcF interval and QTcB interval correction will also be presented, based on the number and percentage of patients meeting or exceeding specific thresholds for absolute QTcF/QTcB interval prolongation and change from baseline in QTcF/QTcB interval. In this analysis, the mean of the triplicate measurements will not be used; instead, the maximum at each timepoint will be considered.

For absolute QTcF/QTcB interval prolongation, the number and percentage of patients within the following thresholds will be summarized at each visit. The worst (largest) value will also be summarized.

- Interval ≤ 450 ms
- Interval >450 ms and ≤ 480 ms
- Interval >480 ms and ≤ 500 ms
- Interval >500 ms

The change from baseline in QTcF/QTcB interval to the worst (largest) post-baseline observation and at each study visit will also be summarized, considering the following thresholds:

- Interval increased from baseline ≤ 30 ms
- Interval increased from baseline >30 ms and ≤ 60 ms
- Interval increased from baseline >60 ms

For the analysis of change from baseline, the mean of the triplicate measurements will be used for all visits. In the categorical analyses, the maximum of triplicate measurements will be used for post-baseline values.

These summary tables will be presented by timepoint, and for the maximum post baseline value.

All summary outputs for ECG will consider central ECG data.

All ECG data will be provided in a by-patient listing. Local ECG data will be listed only.

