6.4.6. Laboratory Parameters

Baseline values and values at each visit for each laboratory parameter collected will be descriptively summarized.

Laboratory data will also be summarized using shift tables where appropriate. Each patient's continuous laboratory safety parameter values will be flagged as "low", "normal", "high" or "missing" relative to the normal ranges. Each patient's categorical laboratory safety parameter values will be flagged as "abnormal" or "normal". This categorical data will be summarized in shift tables comparing the minimum post-baseline value, maximum post-baseline value and all other relevant post-baseline visits with those at the baseline visit. Note that minimum post-baseline will only be displayed in the instances where there is a range with $LLN > 0$.

In addition, CTCAE grade and hyperphosphatemia grade will be summarized. Shift tables of grade from baseline to maximum or minimum on-treatment as applicable will be produced. This analysis will also be produced considering cycle 1 only.

Laboratory results will be included in by-patient listings and will include CTCAE grade and hyperphosphatemia grade at each visit, as well as change from baseline at each visit.

Hy's law

Subjects who have elevated ALT, AST, and total bilirubin post baseline will be summarized descriptively as follows and Hy's law cases identified.

- ALT and AST: $> 3x$ Upper Limit of Normal (ULN), $> 5x$ ULN, $> 10x$ ULN, $> 20x$ ULN
- Total bilirubin $> 2x$ ULN
- ALT or AST: $> 3x$ ULN and Total bilirubin $> 2x$ ULN

Plots of ALT and AST vs. Total bilirubin by module will also be produced with reference lines at $3 \times ULN$ for ALT, AST, and $2 \times ULN$ for total bilirubin. In each plot, peak total bilirubin $\times ULN$ will be on the vertical axis and peak ALT or AST $\times ULN$ will be on the horizontal axis.

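### The SAP's listings-only default for unscheduled visits has no written exception for the worst-value laboratory, Hy's law and QTc summaries, so these can understate toxicity

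*SAP*

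**What the plan says.** SAP 6.1.3 (Visit Windows) tabulates data under the visit recorded on the eCRF and then adds: "Unless otherwise stated in the analysis sections below, unscheduled visits will be included in data listings only". An off-schedule result therefore reaches a table only if a later section admits it.

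SAP 6.4.6 asks for laboratory shift tables "comparing the minimum post-baseline value, maximum post-baseline value and all other relevant post-baseline visits" with baseline. On toxicity grade it says: "Shift tables of grade from baseline to maximum or minimum on-treatment as applicable will be produced". It also asks for counts of patients above multiples of ULN for ALT, AST and bilirubin, identification of Hy's law cases, and plots of peak ALT or AST against peak bilirubin. For QTcF and QTcB thresholds, SAP 6.4.5 says: "The worst (largest) value will also be summarized". Neither section mentions unscheduled results.

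The protocol calls for testing between scheduled visits:
- Section 5.3.2.5: for unexplained abnormal laboratory values, "the tests must be repeated immediately and followed-up until return to the normal range", or until they stabilize or are explained.
- Section 6.1.1.5, Table 5: weekly reassessment while derazantinib is withheld for hyperphosphatemia.
- Section 6.1.1.5.3: after a QTcF of at least 501 ms on two or more ECGs, "hourly (triplicate) 12-lead ECG obtained until the mean QTcF has returned".
- Section 6.4.2: liver function tests every 4–5 days if drugs with known liver toxicity are co-administered.

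**The concern.** A worst-value table exists to show how far each patient's result went, whatever the visit. If it draws only on scheduled visits, it leaves out the tests most likely to be done because something is wrong.

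This matters most for the liver. Transaminase elevation is derazantinib's one important identified risk (Protocol 1.5.1 and 7.1.1.2), and meeting Hy's law criteria in Cycle 1 is a dose-limiting toxicity in Substudies 3 and 5 (Protocol 7.3.3). A Hy's law count that can omit repeat tests is a weak basis for a safety conclusion. Hyperphosphatemia grade and QTc thresholds are exposed to the same rule.

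**Working it through.** The plan states no figure on this point, so the check has three parts: whether any section overrides the default, which way the error runs, and how wide the gap between scheduled tests is.

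**1. Is an exception written?**

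| Summary | SAP section | Exception for off-schedule results |
|---|---|---|
| PFS progression | 6.3.2.3, Tables 5–7 | Yes: progression between scheduled visits counts |
| Time to progression | 6.3.3.1, Table 8 | Yes, same row |
| Laboratory minimum/maximum shifts | 6.4.6 | None |
| Worst CTCAE and hyperphosphatemia grade | 6.4.6 | None |
| Hy's law counts and peak plots | 6.4.6 | None |
| Worst QTcF/QTcB | 6.4.5 | None |

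The SAP provides for off-schedule data explicitly for the progression endpoints. It does not do so for the safety maxima, so the default in 6.1.3 governs them.

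**2. Direction.** Let S be a patient's scheduled post-baseline values and U the unscheduled ones. Then max(S) ≤ max(S ∪ U) and min(S) ≥ min(S ∪ U). Any count of patients beyond a threshold is therefore no larger using S alone. The error is zero when the peak is on a scheduled test and otherwise always understates.

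**3. Width of the gap.** A cycle is 21 days (Protocol synopsis). In Protocol Table 1, scheduled laboratory tests after C1D15 fall on Day 1 of each cycle. For safety interim analysis patients in Substudies 3 and 5, this spacing starts after Cycle 2. Assume an abnormality lasts d days (d ≤ 21) and starts at a random point between scheduled tests. The chance that no scheduled test falls inside it is 1 − d/21:

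- d = 3: 1 − 3/21 = 0.857
- d = 7: 1 − 7/21 = 0.667
- d = 10: 1 − 10/21 = 0.524
- d = 14: 1 − 14/21 = 0.333

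These are shares of episodes invisible to scheduled testing. The SAP rule does harm only in those that an unscheduled test actually caught. It also does harm where a scheduled test was abnormal but the repeat was worse.

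**4. One hypothetical patient.** ALT is 2.8×ULN on a scheduled Day 1. An unscheduled test on day 10 shows ALT 11×ULN with bilirubin 2.4×ULN. ALT is 2.5×ULN on the next Day 1. With scheduled values only, the maximum ALT is 2.8×ULN, so the patient is in no ALT category (the lowest is >3×ULN) and is not a Hy's law case. With all values, the patient is above 10×ULN and meets the SAP's combined criterion (ALT or AST >3×ULN with bilirubin >2×ULN).

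**5. QTc.** Here the effect is smaller. If the triggering ECGs were scheduled, a mean QTcF of at least 501 ms already puts the patient in the top absolute band (>500 ms), and hourly repeats cannot change that. The change-from-baseline bands can still move. A man with a baseline at the 450 ms eligibility limit (Protocol 4.3) and a trigger value of 501 ms has an increase of 501 − 450 = 51 ms. That is below the >60 ms band, which a higher repeat could reach. If the trigger was itself an unscheduled ECG, the absolute band is affected too.

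**The case against.** **Section 6.1.3 may be meant only for by-visit tables.** Its title and first sentence concern visits, and 6.4.5 distinguishes the worst observation from values at each study visit. A programmer could reasonably read a maximum post-baseline value as covering everything. That shows the text is open to a sensible reading, but the reading overrides an explicit rule by inference. Two programmers could produce different Hy's law counts from the same SAP.

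**The values are not lost.** A reader might infer that an off-schedule peak appears in no summary at all. The documents do not support that. Abnormal liver tests, hyperphosphatemia, raised creatinine and QT prolongation are AEs of special interest that must be recorded in the eCRF (Protocol 7.2.6), and SAP 6.4.1 tabulates AEs by patient, not by visit. Laboratory listings carry the grades. This stands, and it limits the damage to the laboratory and ECG tables. It does not remove it: listings give no rates, and Protocol 7.4.3.1.1 makes a laboratory result an AE only if it meets clinical criteria.

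**Repeats follow the trigger value.** Hourly ECGs and weekly phosphate checks start after an abnormal value, and nothing in the protocol says the peak comes later. That is fair. The claim is that peaks can fall there, not that they usually do.

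**Response rate.** A reader might infer that confirmation scans drop out of ORR. Protocol 5.3.3.2.4 asks sites to "perform the confirmation scan of CR or PR 4–5 weeks after the last scan was performed". A first response at week 9 is then confirmed at 9 + 4 to 9 + 5 = weeks 13–14, outside the next scheduled window of weeks 17–19. The documents nevertheless point the other way:
- SAP 6.3.1.1 builds confirmation from BICR assessments at least four weeks apart, not from visits. On a 9- and 12-week grid that minimum has little purpose unless off-grid scans count.
- Protocol Appendix 2 requires the confirmation scan.
- Table 1 footnote 11 refers to it, and footnote 13 allows additional scans per RECIST 1.1.
- Protocol 8.3.4.1 expects up to four post-baseline assessments by about week 27, where the grid gives three (weeks 9, 18 and 27).

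**Conclusion.** The concern holds for the safety summaries. SAP 6.1.3 states a rule, SAP 6.4.5 and 6.4.6 write no exception, and the protocol places required tests outside the schedule. Applied literally, the worst-value, worst-grade, Hy's law and QTc tables can omit peaks found on unscheduled tests and can only understate toxicity.

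The number of patients affected cannot be derived, because the documents give no frequency of unscheduled tests and no duration of abnormalities. The 67% and 33% figures for 7- and 14-day episodes rest on the assumed random onset and are illustrations, not estimates of bias in this trial.

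The rule does not cover all unscheduled data: it carries its own qualifier, and PFS and time to progression use between-visit progression. Baseline is not affected either, since SAP 6.1.1 already takes the last non-missing value before first dose. For ORR the assessment-based confirmation rule already implies that off-grid scans count, so no loss of responders or power is claimed. This should be corrected before the tables are programmed.

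**What to change.** Amend SAP 6.1.3, with a cross-reference in 6.4.5 and 6.4.6, to read along these lines: *Unscheduled results are excluded from by-visit summaries only. They are included in all minimum, maximum and worst post-baseline summaries, worst-grade shifts, Hy's law counts and plots, and QTc threshold summaries.*

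As a clarification only, add to SAP 6.3.1 that all BICR time points, including confirmation scans outside the scheduled grid, count toward response.

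The cost is a few sentences and a programming flag. No new data are needed, and the two-stage decision rules and their error rates are untouched. The downside is that reported worst-case toxicity rates may rise slightly.
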